BLOOM Study

English translation of the original French document.

Research sponsor: Groupe Hospitalier de La Rochelle Ré Aunis

Coordinating investigator: [name] [name]

1. Administrative information

Title/Acronym (will be made public): Real-world data from people with diabetes using closed-loop insulin pump therapy (BLOOM)

Project team: [name] (hospital practitioner) / [name] (PhD) / [name] (clinical research associate)

2. Objectives and purpose

a. Study background and objectives

In recent years, insulin pump systems coupled with continuous glucose sensors enabling semi-automated insulin delivery (closed-loop systems) have been developed.

Their use has been validated in clinical trials, but the international investigation centres participating in these trials are not always representative of French centres, and the patients they manage may also differ. Eligibility criteria in trials are stricter and more restrictive than those in routine practice in diabetology/endocrinology departments. Sociodemographic characteristics of trial participants - notably the male/female ratio, age, and ethnicity - do not necessarily reflect those observed in patients who actually use the device in real-world care.

Our objective is to evaluate, in real-world conditions, the impact of closed-loop systems on improving glycaemic control in people with diabetes managed in diabetology/endocrinology departments of general hospitals.

b. Ethical compliance

The purposes of data processing are defined, explicit and legitimate. An information letter is handed to patients in person or sent by post to their home. The data collected are adequate, relevant, and limited to what is necessary for the study.

c. Public interest justification

This study will measure the effectiveness and risks associated with the use of closed-loop insulin pumps in routine clinical practice.

d. Dissemination and publication

Peer-reviewed scientific article.

3. Methodology

a. Required data sources

- Medical records
- PMSI only
- SNDS extraction
- Registry
- Survey / cohort
- Other: diabetes platforms (CareLink / MyDiabby / YourLoops)

b. Study cohort description

Inclusion criteria:

- Age > 7 years
- Type 1 diabetes
- Equipped with a closed-loop insulin pump

Non-inclusion criteria:

- Presence of a legal protection measure limiting autonomous decision-making
- Patient or legal representative objecting to the use of data for research purposes

c. Methods, data processing and analysis

Data will be collected as follows:

i. At inclusion (baseline)

- Demographics: sex, age, weight, body mass index (automatically calculated).
- Medical history: retinopathy, nephropathy, coronary artery disease, stroke.
- Diabetes-related data: diabetes duration, HbA1c, year of insulin pump initiation, type of glucose monitoring (continuous glucose monitoring [CGM]; e.g., FreeStyle Libre or other - to be specified), year of CGM initiation.
- Data from the diabetes platform (CareLink) for the 3 months prior to closed-loop initiation and the last 14 days: time in range 70-180 mg/dL (TIR), time below range <70 mg/dL (TBR), time above range >180 mg/dL (TAR), mean glucose, coefficient of variation, mean number of capillary blood glucose tests per day, mean total daily insulin dose, basal/bolus ratio, grams of carbohydrates consumed per day.
- Number of severe hypoglycaemic events in the last 12 months.
- Ketosis or diabetic ketoacidosis in the last 12 months.
- Diabetes-related hospitalisations in the last 12 months.
- Device data: date of closed-loop initiation, closed-loop pump brand (MiniMed), configured glucose target, active insulin time in closed-loop mode.

ii. Follow-up at M3 (3 months after inclusion)

- Clinical characteristics: weight, BMI.
- Data from the diabetes platform for the last 14 days: HbA1c, time in SmartGuard, time in temporary basal, time in manual mode, TIR, TBR, TAR, configured glucose target, mean glucose, coefficient of variation,

mean number of capillary blood glucose tests per day, mean total daily insulin dose, basal/bolus ratio, grams of carbohydrates consumed per day.

- Device data: number of sensors used, number of sensor malfunctions; report transmitter and/or pump change if applicable (MiniMed, t:slim, DBLG1).
- Adverse events: number of severe hypoglycaemic events since the previous visit; number of episodes of ketosis or diabetic ketoacidosis since the previous visit; number of diabetes-related hospitalisations since the previous visit; other diabetes-related adverse events.

iii. Follow-up at M6 (6 months after inclusion)

- Clinical characteristics: weight, BMI.
- Data from the diabetes platform for the last 14 days: HbA1c, time in SmartGuard, time in temporary basal, time in manual mode, TIR, TBR, TAR, configured glucose target, mean glucose, coefficient of variation, mean number of capillary blood glucose tests per day, mean total daily insulin dose, basal/bolus ratio, grams of carbohydrates consumed per day.
- Device data: number of sensors used, number of sensor malfunctions; report transmitter and/or pump change if applicable (MiniMed, t:slim, DBLG1).
- Adverse events: number of severe hypoglycaemic events since the previous visit; number of episodes of ketosis or diabetic ketoacidosis since the previous visit; number of diabetes-related hospitalisations since the previous visit; other diabetes-related adverse events.

iv. Follow-up at M12

- Clinical characteristics: weight, BMI.
- Data from the diabetes platform for the last 14 days: HbA1c, time in SmartGuard, time in temporary basal, time in manual mode, TIR, TBR, TAR, configured glucose target, mean glucose, coefficient of variation, mean number of capillary blood glucose tests per day, mean total daily insulin dose, basal/bolus ratio, grams of carbohydrates consumed per day.
- Device data: number of sensors used, number of sensor malfunctions; report transmitter and/or pump change if applicable (MiniMed, t:slim, DBLG1).
- Adverse events: number of severe hypoglycaemic events since the previous visit; number of episodes of ketosis or diabetic ketoacidosis since the previous visit; number of diabetes-related hospitalisations since the previous visit; other diabetes-related adverse events.

v. Follow-up at M18 (end of study)

- Clinical characteristics: weight, BMI.
- Data from the diabetes platform for the last 14 days: HbA1c, time in SmartGuard, time in temporary basal, time in manual mode, TIR, TBR, TAR, configured glucose target, mean glucose, coefficient of variation, mean number of capillary blood glucose tests per day, mean total daily insulin dose, basal/bolus ratio, grams of carbohydrates consumed per day.
- Device data: number of sensors used, number of sensor malfunctions; report transmitter and/or pump change if applicable (MiniMed, t:slim, DBLG1).
- Adverse events: number of severe hypoglycaemic events since the previous visit; number of episodes of ketosis or diabetic ketoacidosis since the previous visit; number of diabetes-related hospitalisations since the previous visit; other diabetes-related adverse events.

vi. Analyses

- Describe demographic and clinical characteristics of the type 1 diabetes population initiated on closed-loop therapy (M0).
- Assess changes in glycaemic control at M3, M6, M12 and M18 versus M0 (TIR, TBR, TAR, HbA1c, mean glucose and glucose coefficient of variation).
- Assess adherence to closed-loop use at M3, M6, M12 and M18 (percentage of time in SmartGuard, manual mode, on closed-loop pump, and reasons for discontinuation).
- Assess changes in insulin requirements at M3, M6, M12 and M18 versus M0 (mean total daily insulin dose, basal/bolus ratio, carbohydrate intake).
- Assess safety (number of diabetes-related hospitalisations, diabetic ketoacidosis, severe hypoglycaemia) and device vigilance (pump/transmitter changes, number of sensors used, defective sensors) at M3, M6, M12 and M18.
- Assess self-monitoring practices at M3, M6, M12 and M18 (mean number of capillary blood glucose tests).

d. Data flow and record linkage

Data will be extracted from the electronic medical record and the closed-loop device software (CareLink, MyDiabby, YourLoops) and entered into an eCRF.

Data in the eCRF will be pseudonymised. The paper correspondence table (re-identification key) will be kept at the investigator site and destroyed after acceptance of the publication.

The database will be transferred to the statistician for analysis via a secure channel. It will then be stored and archived on the clinical research department server.

Only aggregated data will be presented in the study report and scientific publications.

e. Planned timeline and feasibility

- May-August 2022: preparation of study documents, selection of participating centres, and design of the eCRF.
- September 2022: study initiation.
- September 2022-August 2023: retrospective data collection for patients already using closed-loop pumps, and prospective inclusion of patients newly initiated on closed-loop therapy.
- A one-month delay between sending information letters and starting data collection will be respected.
- September 2023-January 2025: follow-up of prospectively included patients.
- February-March 2025: data analysis.
- April-May 2025: manuscript drafting.
- Mid-2025: submission.

4. Privacy, security and confidentiality of data

a. Patient information and protection of rights

Individual information of patients/service users, etc.

Collective information

Data media and security

Request for exemption from individual information (to be justified):

5. References

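### Impact is judged by uncontrolled change versus an M0 of undefined timing, with no use of the pre-initiation course, so regression to the mean and prior trends cannot be separated from a closed-loop effect

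*Combined protocol and SAP*

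**What the plan says.** The aim in section 2.a is to evaluate "the impact of closed-loop systems on improving glycaemic control in people with diabetes managed". Section 2.c adds: "This study will measure the effectiveness and risks associated with the use of closed-loop insulin pumps in routine clinical practice". Both are causal statements.

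Section 3.b makes "Equipped with a closed-loop insulin pump" an inclusion criterion. All participants are therefore users and no comparator is described. No HbA1c or time-in-range (TIR) threshold is set for entry.

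Section 3.c.i lists HbA1c once: "Diabetes-related data: diabetes duration, HbA1c, year of insulin pump initiation". It gives no date window and does not say that the value precedes initiation. Platform data are listed "for the 3 months prior to closed-loop initiation and the last 14 days", which is two windows. Severe hypoglycaemia, ketosis or ketoacidosis, and hospitalisations have 12-month look-backs. HbA1c does not.

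The glycaemic analysis in 3.c.vi is one line: "Assess changes in glycaemic control at M3, M6, M12 and M18 versus M0". It gives no model, adjustment or pre-initiation term. The same section links M0 to starting closed loop, whereas 3.c counts the M3 and M6 visits from inclusion. Section 3.e brings in both existing users, collected retrospectively, and new starters, included prospectively.

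**The concern.** Without a comparator, a change from M0 mixes the device effect with anything else that moves glycaemia over the same 18 months. Two sources matter most. If patients tend to be offered closed loop after a poor spell, later values would improve somewhat without it. If control was already improving or worsening, for example in children and adolescents (entry is from age over 7), that drift is included in the M18 change.

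Each patient's own course before initiation is the one internal control this design can offer. The plan uses medical records and obtains three months of pre-initiation platform data, but it collects no earlier HbA1c and plans no look at change before M0.

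The undefined M0 adds a third problem, which can act the other way. For someone already on closed loop at inclusion, an HbA1c taken at inclusion, or the most recent 14 days, could fall after initiation and hide part of a real change. What is at stake is the conclusion about impact and effectiveness. The descriptive results would survive.

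**Working it through.** **Inputs.** The documents give no sample size, SD, expected effect, correlation or significance level, so there is no plan figure to reproduce. Every input below is an assumption: HbA1c SD 1.0 point, TIR SD 15 points, correlation between repeat values ρ = 0.7 to 0.9, SD of HbA1c change 0.8.

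**1. Regression to the mean.** With no treatment effect, expected change = (1 − ρ) × (group mean at M0 − mean of the population the group was selected from). The reference has to be the source population. If the distance were measured from these patients' own long-run level, the whole distance would be the artefact. For a shift of k SDs towards poor control, the spurious improvement is:

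| k | HbA1c points: (1 − ρ) × k × 1.0 | TIR points, 14-day M0: (1 − ρ) × k × 15 |
|---|---|---|
| 0 | 0 | 0 |
| 0.25 | 0.025 to 0.075 | 0.375 to 1.125 |
| 0.5 | 0.05 to 0.15 | 0.75 to 2.25 |
| 1.0 | 0.10 to 0.30 | 1.5 to 4.5 |

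The signs reverse if patients are chosen for good control.

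**2. Which platform window is M0.** Averaging m = 90/14 = 6.43 windows gives reliability R = mρ / (1 + (m − 1)ρ) (Spearman-Brown). For ρ = 0.7, R = 4.5/4.8 = 0.9375. For ρ = 0.9, R = 0.983. At k = 0.5 the TIR artefact is (1 − R) × 7.5, or 0.47 and 0.13 points, against 2.25 and 0.75 with a 14-day M0. This is a best case, since it treats the 14-day windows as independent. The choice that the plan leaves open therefore matters.

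**3. Prior trend.** A steady TIR trend of t points per year contributes t × 18/12 at M18: 1.5, 3 and 6 points for t = 1, 2 and 4, in either direction.

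**4. M0 after initiation.** If a share p of participants have an M0 value that already contains the full effect, the mean change shrinks to (1 − p) times the true one.

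**5. Would an artefact look like a finding?** Suppose there is no device effect, an artefact of 0.15 HbA1c points, and a two-sided 5% paired test. With z = 0.15 / (0.8/√n), the probability of significance is about Φ(z − 1.96). For n = 100, z = 1.875 and the probability is 47%. For n = 50, 200 and 300 it is 26%, 76% and 90%.

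**6. Which pre-initiation analysis helps.** Suppose only M0 is raised, by e, and single values have independent errors of SD s.

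- *Change versus M0:* artefact e, reference SD s.
- *Line fitted through M−12, M−6 and M0, projected to M18:* slope = 6e/72 = e/12 per month and fitted mean = e/3 at M−6. The projection is e/3 + 24 × e/12 = 2.33e, with SD s × √(1/3 + 24²/72) = 2.9s. The artefact more than doubles.
- *Mean of M−12 and M−6:* artefact 0, SD s/√2 = 0.71s. This reference is centred at M−9, so a linear drift enters the M18 contrast over 27 months instead of 18, which is 1.5 times as much.

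The mean of the earlier values thus guards against a raised M0 but not against drift. The M−12 to M0 change has to be read beside it.

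**The case against.** The strongest reply is that this is a deliberate real-world cohort. Section 2.a says the systems are already validated in trials and that the gap is representativeness, and 3.c.vi speaks only of describing and assessing changes. That stands as a defence of the single-arm design. It does not cover the causal wording of 2.a and 2.c, which nothing in 3.c.vi can support.

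A reader might infer that the plan reduces the platform baseline to a single level. It does not: two windows are listed, and the three-month one averages out much short-term noise. For a new starter, the last 14 days may itself be a pre-initiation window. What is missing is the choice of M0 and any use of the data as a course over time.

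A reader might also infer that regression to the mean and prior trends will certainly be credited to the device. The documents do not support that. Entry has no glycaemic threshold, so the bias could be near zero or reversed, and an M0 HbA1c taken after initiation in existing users would pull the change towards zero. The documents do not even establish that the one listed HbA1c precedes initiation.

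Finally, section 2.b commits to collecting only necessary data. Two dated HbA1c values serve the stated objective directly, so they can be justified under that commitment.

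**Conclusion.** The concern holds in a limited form. Impact and effectiveness are to be read from uncontrolled change versus an M0 that is not defined for each outcome, and no analysis uses the pre-initiation course. Regression to the mean and pre-existing trends therefore cannot be separated from a closed-loop effect. The documents do not show that either is present.

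On the assumed inputs, regression to the mean ranges from 0 to 0.30 HbA1c points, or 0 to 4.5 TIR points with a 14-day M0, and the direction could reverse. A prior TIR trend of up to 4 points per year would add up to 6 points at M18. These figures show what the design cannot rule out and are not estimates for this cohort. The plan should be changed on this point. The description of what happens after initiation remains valid without the change, provided M0 is fixed before initiation.

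**What to change.** **In 3.c.i:** require the M0 HbA1c to be dated and to precede closed-loop initiation. Name the pre-initiation platform window that serves as M0. Add the dated HbA1c values nearest 12 and 6 months before initiation, taken from the medical records already in use.

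**In 3.c.vi:** report the pre-initiation change (M−12 to M0) beside the post-initiation change. Add a sensitivity analysis comparing follow-up HbA1c with the mean of the M−12 and M−6 values, which is less exposed to a raised M0. Do not extrapolate each patient's fitted pre-initiation slope, for the reason in step 6 of the working.

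**In 2.a, 2.c and the report:** word conclusions as change after initiation, not impact or effectiveness, where the pre-initiation data are missing or do not support a causal reading.

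**Cost:** two extra HbA1c values per patient, dates for all HbA1c values used, and two short additions to the analysis, with no new visits. Earlier values will be missing for some newly referred patients, probably not at random, so their number should be reported. The reported effect may turn out smaller.

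### Change in insulin requirement is measured by a daily dose not standardised for weight in a cohort that admits growing children, so growth can read as a rising requirement

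*Combined protocol and SAP*

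**What the plan says.** The analysis list in section 3.c.vi includes: "Assess changes in insulin requirements at M3, M6, M12 and M18 versus M0 (mean total daily insulin dose", followed in the same bracket by the basal/bolus ratio and carbohydrate intake. Of these three measures, daily dose is the only one that gives the amount of insulin used. Sections 3.c.i to 3.c.v collect it in the same form, within the platform items "mean number of capillary blood glucose tests per day, mean total daily insulin dose, basal/bolus ratio, grams of carbohydrates consumed per day". The documents state no unit for it, and they contain no per-kilogram version, no weight adjustment and no age stratum.

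Section 3.b sets a lower age limit of 7 years and no upper limit. Its non-inclusion criteria include "Patient or legal representative objecting to the use of data for research purposes", which is consistent with enrolling minors.

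Weight is collected throughout. At baseline the entry is "Demographics: sex, age, weight, body mass index (automatically calculated". At M3, M6, M12 and M18 it is "Clinical characteristics: weight, BMI". The last time point is "Follow-up at M18 (end of study". None of the listed analyses relates weight to dose.

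**The concern.** The bullet's stated target is insulin requirement. A child who grows over 18 months needs more insulin per day even when the need per kilogram has not moved. Measured by unscaled dose, that growth is counted as a change since M0. With no comparison group described, the unscaled dose alone cannot separate growth from an effect of closed-loop therapy.

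The direction is predictable. In children the distortion is towards an apparent rise, it increases with follow-up, and it is largest at M18. A real reduction in requirement could be reported as no change or as an increase. The size in the whole cohort depends on how many participants are still growing, which the plan neither states nor provides a way to show.

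**Working it through.** The documents give no effect size, standard deviation or sample size for this analysis, so there is no planned figure to reproduce. What follows is an illustration.

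**Inputs from the documents:** follow-up of 18 months (1.5 years); minimum age of 7 years; weight listed at all five time points.

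**Assumed inputs:** child of 30 kg at M0; requirement constant at 0.8 U/kg/day; weight gain of 2.5 to 4 kg/year; adults stable at 45 U/day (for example 75 kg × 0.6 U/kg/day).

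**1. Within one child.** Dose at M0 = 0.8 × 30 = 24 U/day. Rise by M18 = requirement × yearly gain × 1.5:
- low: 0.8 × 2.5 × 1.5 = 3.0 U/day, and 3.0/24 = 12.5%
- high: 0.8 × 4 × 1.5 = 4.8 U/day, and 4.8/24 = 20%

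The percentage is simply the percentage weight gain, so it does not depend on the 0.8. On the U/kg/day scale the change is zero by construction.

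**2. What could be masked.** A fall in need per kilogram of 1 − 1/1.125 = 11.1% to 1 − 1/1.20 = 16.7% would be exactly offset by this growth and would appear as no change at M18.

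**3. Pooled mean.** Spurious change = share × rise / (share × 24 + (1 − share) × 45).

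| Share of children | M0 mean (U/day) | Rise (U/day) | Rise (%) |
|---|---|---|---|
| 10% | 42.9 | 0.30 to 0.48 | 0.7 to 1.1 |
| 30% | 38.7 | 0.90 to 1.44 | 2.3 to 3.7 |
| 50% | 34.5 | 1.50 to 2.40 | 4.3 to 7.0 |

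**4. Older adolescents.** Keep the 10% share, but let half of the minors weigh 60 kg, gain 1.5 kg/year and need 0.8 U/kg/day. Their dose is 48 U/day and rises by 0.8 × 1.5 × 1.5 = 1.8 U/day. The M0 mean is 0.05 × 24 + 0.05 × 48 + 0.90 × 45 = 44.1 U/day. The rise is 0.05 × 3.0 + 0.05 × 1.8 = 0.24 to 0.05 × 4.8 + 0.05 × 1.8 = 0.33 U/day, or about 0.5% to 0.75%.

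**5. Other growth assumptions.** For children of 25 kg gaining 2.5 kg/year, 30 kg gaining 3, 40 kg gaining 5 and 50 kg gaining 6, the M18 rise (yearly gain × 1.5 / starting weight) is 15.0%, 15.0%, 18.8% and 18.0%. Pooled with adults at 45 U/day, the lowest and highest cases run were:
- 30 kg gaining 3 kg/year at 0.8 U/kg/day: with 5% children, 0.18/44.0 = 0.4%; with 50%, 1.8/34.5 = 5.2%
- 50 kg gaining 6 kg/year at 1.0 U/kg/day: with 5% children, 0.45/45.2 = 1.0%; with 50%, 4.5/47.5 = 9.5%

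**The case against.** **Materiality.** The strongest objection is that the pooled result may hardly be affected. Section 2.a places the study among "people with diabetes managed in diabetology/endocrinology departments of general hospitals", and the medical history collected includes coronary artery disease and stroke. Both are compatible with a mostly adult cohort, though they do not prove one. At a 10% share the distortion is about 1% or less. The stated objective is glycaemic control, and insulin requirement is one of six analysis bullets with no test or decision attached. This stands, and it limits the weight of the point. It does not help anyone who reads the results for children, where the distortion is 12.5% to 20% under the assumed inputs.

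**Choice of scale.** Dose per kilogram is not a clean replacement. Follow-up weight is measured after treatment starts. If closed-loop therapy changes adult weight, dividing by it absorbs part of a device-related change in dose. Need per kilogram may also change with age in children, so U/kg removes body size but not every effect of maturation. Both points stand. They argue for reporting both scales and separating age groups, not for leaving the dose unscaled.

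**Data.** Section 3.e includes retrospective collection for patients already on closed loop. Section 3.c.i lists weight at inclusion, while the baseline platform data refer to the period before closed-loop initiation. For these patients the two dates may differ, and routine records may lack a weight. This also stands, and the fix has to deal with it.

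**Stronger readings.** A reader might infer that the plan prescribes analysis in absolute units. It does not: no unit is given, and the most that can be said is that the dose is not standardised for weight. A reader might also infer that the cohort-level dose result is seriously biased, or that U/kg should replace total dose as the only main measure. The first needs a paediatric share that the documents do not give. The second overlooks the adult weight problem above.

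**Conclusion.** The point holds as a cheap improvement to a secondary analysis. The omission is plain from the text: a dose measure without weight scaling, eligibility from childhood, 18 months of follow-up, no comparison group described, and weight listed at every time point but not used with the dose.

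The size is conditional. Within growing children the distortion is material on any of the assumed inputs, at about 12.5% to 20% by M18. In the pooled mean it runs from about 1% or less with 10% children to 4% to 7% with 50%. It is lower if many minors are near adult size, and reaches 9.5% at a 50% share under the fastest growth and highest requirement tried. All weights, growth rates and requirements are assumptions, as are a constant need per kilogram and stable adult weight. The glycaemic measures are not touched by this point, and the basal/bolus ratio is not directly scaled by body size.

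**What to change.** In the insulin-requirement bullet of section 3.c.vi:

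- Report total daily insulin in U/kg/day alongside total daily dose, at M0 and at each follow-up.
- Show participants under 18 separately from adults.
- Use the weight closest to the dose window. For M0, use the weight nearest to closed-loop initiation, because a retrospective patient's inclusion weight may be from a later date.
- State, for each time point, the number of participants with both weight and dose.
- In adults, interpret U/kg/day together with the unscaled dose.

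The cost is a few lines of analysis wording and an extra set of table rows. No new variable is needed, since weight is already listed at all five time points, but for retrospective patients the M0 weight may have to be looked up at a specific date. Some observations may be lost from the U/kg result where weight is missing. Because the unscaled dose is kept, nothing now planned is lost.

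### M0 has two unreconciled time origins for patients already on a loop, their adherence from initiation is likely biased upward, and discontinuation has no listed date or reason

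*Combined protocol and SAP*

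**What the plan says.** **Who enters.** Section 3.e of the combined protocol and SAP gives two routes between September 2022 and August 2023: "retrospective data collection for patients already using closed-loop pumps", and prospective inclusion of new starters. The only device criterion in 3.b is "Equipped with a closed-loop insulin pump". After August 2023, 3.e schedules follow-up (September 2023 to January 2025) for the prospective patients.

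**When time starts.** Section 3.c.i places baseline at inclusion. Section 3.c.ii is headed "Follow-up at M3 (3 months after inclusion", and 3.c.iii counts M6 in the same way. Sections 3.c.iv and 3.c.v give no origin for M12 and M18. Yet 3.c.i takes platform baseline data from the three months before loop start, plus a 14-day window with no reference date, and it records the "date of closed-loop initiation". Section 3.c.vi describes the "population initiated on closed-loop therapy (M0").

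**What is recorded about stopping.** The adherence analysis in 3.c.vi covers SmartGuard time, manual-mode time, time on the loop pump and the reasons patients stopped. Each list from M3 to M18 has "time in SmartGuard, time in temporary basal, time in manual mode" over 14 days, and "report transmitter and/or pump change if applicable (MiniMed, t:slim, DBLG1").

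**The concern.** Section 2.a justifies the study by trial participants differing from routine users, and adherence, discontinuation and change in glycaemic control are among its named analyses. For a new starter, inclusion and initiation can coincide. For a patient already on a loop they do not, and the choice between them decides what each result means.

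On one clock, a before-and-after comparison can become on-loop against on-loop. On the other, the patients followed from initiation are those who still had the device when identified, although the analysis list speaks of those who started. Separately, a planned analysis of discontinuation without a listed stop date or reason may not be possible in either group: a stopper whose uploads end looks the same as a patient with missing data. No analysis item separates the two groups, so retrospective results would blend into the prospective ones.

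**Working it through.** The plan states no sample size, stop rate or adherence target, so there is no figure to reproduce. The inputs are the dates in 3.e (retrospective collection taken as 1 September 2022 to 31 August 2023) and the visit rules in 3.c.

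**1. Clock starting at inclusion.** The earliest retrospective inclusion is 1 September 2022.
- M3 = 1 December 2022 and M6 = 1 March 2023, both inside the window.
- M12 = 1 September 2023, one day after the window closes.
- M18 = 1 March 2024, also after it.

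Take a patient who started on 28 February 2022 and was included on 1 September 2022. M3 falls on 1 December 2022, about 9 months after starting. HbA1c at inclusion comes after about 6 months of loop use, while the platform baseline may still be the three months before starting. HbA1c and time in range would then have different baselines in the same patient.

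**2. Clock starting at initiation.** Assume identification begins on 1 September 2022. For a visit at month v, the latest start giving that visit by 31 August 2023 is 31 August 2023 minus v months. The minimum time before identification is 1 September 2022 minus that start, or about zero if that start falls later.

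| Visit | Latest start | Minimum time before identification |
|---|---|---|
| M18 | 28 February 2022 | about 6 months |
| M12 | 31 August 2022 | about 0 |
| M6 | 28 February 2023 | about 0 |
| M3 | 31 May 2023 | about 0 |

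In that time, giving up the pump would have kept the patient out. These are minima. A patient who started by 1 March 2021 (1 September 2022 minus 18 months) had all 18 months before identification. If identification came through letters sent in August 2022, one month before collection as 3.e requires, the M18 minimum is about 5 months.

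**3. Direction.** A person who has given up the device has no further loop time. Leaving such people out can only raise mean loop time, or the share still on the loop, relative to all who started. The size depends on the stop rate and the retrospective share, and neither is stated.

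**4. Planned analysis against listed items.**
- SmartGuard and manual-mode percentages: listed, so this part can be done.
- Time on the loop pump: only partly derivable, from those percentages and the pump-change item.
- Stop date, stop reason, explicit on/off status: not listed at M3, M6, M12 or M18.

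**The case against.** The strongest reply is that M0 is not undefined. Section 3.c.vi ties it to initiation, the initiation date is collected, and retrospective collection fits that clock naturally. This stands as far as it goes. The fault is that the inclusion-based rule in 3.c.ii and iii is not reconciled with it.

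Second, the selection argument leans on fine wording in a translated document. Being equipped is wider than using, no text bars past users, and 2.a speaks of "patients who actually use the device in real-world care", which could make continuing users the target. Part of this stands. Patients still equipped but back in manual mode can enter and remain visible, and so do stops after identification. But nothing brings in those who gave up the device earlier, and the analysis list names the initiated population.

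Third, a reader might infer that the retrospective group yields no M12 or M18 at all on the inclusion clock. That rests on one timeline line, which schedules prospective follow-up without prohibiting any other. The supported statement is that none is scheduled for this group.

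Fourth, a reader might infer that loop status and stop reasons are not collected. A partial status can be derived, the medical record is a named source and the eCRF is not shown. Only 'not listed' is supported.

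Fifth, the 6-month figure concerns one visit of four and an assumed identification date; patient lists drawn up earlier would lower it. This stands.

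**Conclusion.** The point holds in three parts, and should be fixed.

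1. M0 has two unreconciled anchors. Following the inclusion rule literally gives existing users an on-loop baseline HbA1c and mistimed visits, so their change from M0 does not measure the effect of starting.
2. On the initiation clock, retrospective adherence is likely biased upward relative to everyone initiated. The problem is largest at M18. The 6-month minimum there is conditional on identification beginning in September 2022, and it concerns giving up the pump, not a return to manual mode.
3. The discontinuation analysis has only partial listed inputs for status and none for date or reason, in both groups.

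It would go too far to attach a percentage to the adherence bias, or to conclude that the glycaemic results are inflated by the missing stoppers. That would depend on how stoppers' glycaemia differed, which the documents do not show. Confidence is medium, because part 2 rests on how broadly 'equipped' was applied.

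**What to change.** - Set M0 at the date of closed-loop initiation for both groups, count all visits from it, and take baseline values, including HbA1c, from before that date.
- Define the retrospective group as all patients started on a closed loop at the centre from a stated date, whether or not still using it. If past users cannot be traced, take adherence and discontinuation from prospective patients only, and state that retrospective results apply to continuing users.
- Report retrospective and prospective patients separately for adherence and change from M0, with the number contributing at each visit.
- Add stop date and stop reason to the listed items, obtained from the medical record where available. Section 3.d keeps the re-identification key until the publication is accepted, so records can be revisited until then.

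The cost is a sentence each for M0 and eligibility, two added items and split tables. Sites must also search initiation lists and send past users the information letter, with the planned one-month delay. If collection is already complete, this means some re-abstraction; the fallback in the second item avoids tracing past users.
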